**Effects of High Intensity Stepping Training on Gait in Patients with Ataxia**

**NCT06450457**

**Version Date: 03/05/2024**

Protocol Title:	Effects of High Intensity Stepping Training on Gait in Patients with Ataxia
Principal Investigator:	[name], PT, DPT
Co-Investigators:	With increased patient volumes, other therapists will be added to the study
Population:	15 patients of ages 18-65 years old with diagnoses of cerebellar ataxia
Number of Sites:	TIRR Memorial Hermann TMC and TIRR Kirby Glenn outpatient
Study Duration:	5 months spanning the months of January to May.
Subject Duration:	At least 3 weeks with patients receiving 1 hour and 30 minutes of non-consecutive stepping intervention per week.

### General Information

|€ The study will be a quantitative, prospective case series and data will be collected for about four months. Patients from TIRR Memorial Hermann TMC and from TIRR Memorial Hermann Kirby Glenn with ataxia from a cerebellar disease, brain injury, or stroke will be recruited and will receive an intervention consisting of high intensity stepping training from a physical therapist. The patientâ€™s Six Minute Walk Test, 10 Meter Walk Test, Scale for Assessment and Rating of Ataxia (SARA), and Berg Balance Scale will be collected before and after intervention.

### Background Information

|€ Ataxic gait is characterized by a disordered coordination between the head, trunk, and legs. This results in impairments in posture, balance, and coordination. Motor training and potentially motor learning in these patients is limited due to involvement of the cerebellum, which is critical in motor adaptation and learning.

|€ Cerebellar ataxia normally manifests itself as decreased coordination leading to increased fall risk, decreased quality of life, and decreased independence. While disorders such as stroke, TBI, and SCI have a CPG that instructs best practices and interventions, patients with cerebellar involvement do not have the same interventional best practices. There is currently low to moderate grade evidence that supports the use of therapeutic exercises for improvement in objective measures such as the SARA and Berg Balance Scale (BBS) in patients with ataxia. Additionally, there is some support for the use of robot assisted walking and treadmill training for patients with ataxia. In terms of intensity, there is a study published from Barbuto et al that suggests that intensity may lead to improvements in SARA, walking speed, Timed up and Go Test, and Dynamic Gait Index. However, this study only looks at the feasibility of maintaining high heart rates in patients that receive stationary bicycle training, not walking interventions. A survey of physical therapists found that while 81% of therapists were interested in ataxia, only 11% of physical therapists

considered themselves as having expertise in treating patients with ataxia. Additionally, two thirds of the physical therapists reported a need for guidelines for treatment of patients with ataxia.

|€ More research needs to be done that specifically examines options for effective therapeutic interventions for patients with cerebellar involvement. The goal of this specific study is to examine the effects of high intensity stepping training on gait recovery, including walking speed and endurance in this population. The hypothesis of the study is that there will be a significant improvement in gait outcome measures (6 Minute Walk Test and 10 Meter Walk Test) in patients who received high-intensity stepping training during therapy. The secondary hypothesis is that the SARA score will not be correlated to improvement in functional outcome measures (such as gait and balance measures) in patients who received high-intensity stepping training during therapy.

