## Objectives

|€ Primary objective: To determine the effects of high intensity stepping training on gait outcome measures in patients with cerebellar ataxia.

|€ Secondary objectives:

- Identify the correlations between gait outcome measures and measures of ataxia and balance in individuals with cerebellar ataxia.
- Determine differences in response to high intensity stepping training based off of diagnosis.

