## Study Design

|€ The study will be a non-blinded prospective case series performed at TIRR Memorial Hermann and TIRR Kirby Glenn. Participants will be recruited if they have an ICD-10 code of ataxia or present with ataxia at initial evaluation. Either the director of the brain injury rehabilitation team or the evaluating therapist will contact the principal investigator in order to refer the patient to the study. The evaluating therapist will provide the PI with the referral through a secure e-mail utilizing their Memorial Hermann e-mail. The secure e-mail will include the patient diagnosis and their room number with no other personal identifiers listed until the patient consents to the research study.

|€ The study sample will be about 15 and the expected duration of the study will be at least 3-4 weeks.

|€ The primary outcomes measured include the 10 Meter Walk Test and the 6 Minute Walk Test. These outcome measures will be performed once at baseline and again at week 3.

|€ The secondary outcomes to be measured include the SARA and the Berg Balance Scale. These outcome measures will be performed once at baseline and again at week 3.

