## Statistics

- |€ Statistics will be utilized to compare outcome measures before and after the intervention. A dependent sample t-test will be used for comparison of pre- and post-intervention outcomes. MANOVAs will be utilized in order to determine potential differences in outcomes in patients with different diagnoses (ie grouping patients based on chronicity, nature of cerebellar disease) and to compare the four outcome measures that I will utilize. I may also consider doing multiple t-tests or multiple ANOVAâ€™s if the data does not meet statistical assumptions. However, I would just need to account for increased possibility of type 1 error.
- |€ Sample size will be 15 patients.

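### No planned analysis estimates the correlations that the secondary objective and hypothesis need, and about 15 patients cannot support a conclusion of no correlation

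*Combined protocol and SAP*

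**What the plan says.** Two places in the combined protocol and SAP call for a correlation. The Background Information section gives the secondary hypothesis: "The secondary hypothesis is that the SARA score will not be correlated to improvement in functional outcome measures". It offers gait and balance measures as examples of those outcomes. The first secondary objective, under Objectives, is: "Identify the correlations between gait outcome measures and measures of ataxia and balance in individuals with cerebellar ataxia".

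The Statistics section names these analyses:

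- A paired comparison over time: "A dependent sample t-test will be used for comparison of pre- and post-intervention outcomes".
- A multivariate comparison by diagnosis: "MANOVAs will be utilized in order to determine potential differences in outcomes in patients with different diagnoses".
- A second use of MANOVA: "and to compare the four outcome measures that I will utilize".
- Several t-tests or ANOVAs as a fallback if assumptions fail, with a remark that type 1 error would then need attention.

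Under Study Design, the secondary outcomes are "the SARA and the Berg Balance Scale. These outcome measures will be performed once at baseline and again at week 3". On size, Statistics says "Sample size will be 15 patients" and Study Design says "The study sample will be about 15". The plan states no significance level, confidence interval or margin for a negligible correlation, and no basis for the number 15.

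**The concern.** If the Statistics section is followed exactly, the first secondary objective and the only secondary hypothesis end without an estimate. The analyst would have to choose a method, and a version of SARA, after the data are in. The choice of SARA matters. Baseline SARA asks whether severity predicts response; change in SARA asks whether ataxia and function improve together. These are different questions.

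The form of the hypothesis adds a second difficulty. It predicts no correlation, so a small sample works in its favour: the fewer the patients, the more likely a non-significant result, whatever the truth. A reader could take that result as confirmation when it shows little more than imprecision.

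**Working it through.** **Step 1: match each question to a method.**

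- Paired t-test: compares the mean of one measure before and after. It says nothing about whether patients with higher SARA improve more or less.
- MANOVA by diagnosis: compares mean vectors between groups. SARA enters at most as one of the outcomes.
- MANOVA across the four measures: the nearest text to a correlation. Its calculation uses covariances among outcomes, but its result is a test of means, and the plan asks for no coefficient from it.
- Fallback t-tests or ANOVAs: comparisons of means again.

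No named method gives an estimate of association.

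**Step 2: identify the variables.** With SARA taken at baseline and at follow-up, the phrase in the hypothesis could mean the baseline, final or change score. The hypothesis speaks of improvement, whereas the objective does not mention change, so the two do not describe the same quantity.

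**Step 3: what 15 patients could show if a correlation were added.** The plan's 15 has no derivation, so there is no figure to reproduce.

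Inputs: n = 15 from Statistics. Assumptions not in the documents: two-sided 0.05, bivariate normality, a Pearson coefficient, and 12 or 10 completers as a range, since no dropout rate is stated.

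*Smallest significant correlation*, t/√(n−2+t²). For n = 15, t on 13 df is 2.160, so 2.160/√(13+4.667) = 0.514.

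*95% interval at an observed r of 0*, ±tanh(1.96/√(n−3)). For n = 15, tanh(1.96/√12) = tanh(0.566) = 0.512.

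*95% interval at an observed r of 0.3*, n = 15: tanh(0.310 ± 0.566) = −0.25 to 0.70.

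*Chance that a true correlation is non-significant*, approximately 1 − Φ(atanh(ρ)√(n−3) − 1.96). For ρ = 0.5 and n = 15: 0.549 × 3.464 = 1.903; 1.903 − 1.96 = −0.057; 1 − Φ(−0.057) = 0.52. Simulation with 200,000 samples per case gives 0.50. The table uses the simulated values.

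| Completers | Smallest significant absolute r | 95% interval at r = 0 | Non-significant if true r = 0.3 | 0.5 | 0.7 |
|---|---|---|---|---|---|
| 15 | 0.514 | ±0.51 | 81% | 50% | 12% |
| 12 | 0.576 | ±0.57 | 84% | 60% | 22% |
| 10 | 0.632 | ±0.63 | 87% | 67% | 32% |

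Even a sample correlation of exactly zero therefore leaves moderate correlations in either direction within the interval.

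**Step 4: how far to trust these figures.** They are illustrative. The Study Population section allows entry with walk-test values recorded as 0, although it also excludes nonambulatory patients. A cluster of zeros at baseline would make normality doubtful. A Spearman coefficient suits such data better and would be similarly or slightly less precise.

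**The case against.** The best defence is that this is a small, unblinded case series, the hypothesis is secondary, and a correlation is plainly implied by the objective. The small size is a fair reason to ask for nothing elaborate. It does not excuse the gap, because the section names its other methods, and an implied correlation still leaves the coefficient, the SARA variable and the pairs open.

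A second defence is that the figures in the working rest on assumptions the plan does not make. That is correct. The missing analysis and the undefined SARA variable stand on the text alone; only the size of the imprecision depends on the assumptions.

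Three stronger readings are tempting and should be resisted:

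- *The investigators will report a non-significant correlation as no correlation.* The plan does not say so. The risk comes from how the hypothesis is worded and is conditional on how the result is read.
- *The study could detect no correlation at all.* With 15 completers, a true correlation of 0.7 would be missed only about 12% of the time. The weakness concerns moderate and small correlations.
- *The end of the improvement period is also undefined, because Study Design says week 3 and Study Procedures says discharge.* Those passages do need to be reconciled, but that is a separate point. The wording covers the primary walk tests as well, so it is not specific to the correlation, and discharge may simply mean the end of the three-week course. The study schedule listed under Attachments might settle it.

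**Conclusion.** The point holds. The plan has a correlation objective and a hypothesis of no correlation, names no analysis that estimates a correlation, and does not define which SARA score is meant. None of this depends on an assumption.

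Because the hypothesis is one of absence without a margin, about 15 patients cannot support it. Under the stated assumptions, the interval around a zero correlation reaches about 0.51 in each direction, and a true correlation of 0.5 would be non-significant in 50% to 67% of studies with 15 down to 10 completers.

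This should be corrected, but it is a secondary matter. The missing correlation analysis and the undefined SARA variable do not bear on the paired comparison of the walk tests. That is not a finding that the primary comparison is free of other problems.

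**What to change.** In Background Information, restate the secondary hypothesis as estimation of the association between baseline SARA and change in the six-minute walk, the ten-metre walk and the Berg Balance Scale. If change in SARA is what is meant, say so before any data are analysed.

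In Statistics, add Spearman correlations with 95% confidence intervals for:

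- baseline SARA against each of those three change scores (3 pairs);
- for the first secondary objective, the two walk tests against SARA and the Berg Balance Scale at baseline (2 × 2 = 4 pairs). The objective names no time point; baseline is proposed here so that one is fixed in advance.

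Label all seven exploratory, which also deals with their number, and state that a non-significant correlation will not be reported as absence of correlation.

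The cost is one reworded sentence and a short paragraph, using data already to be collected. The downside is a less definite secondary claim, with wide intervals in plain view.

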## Objectives

|€ Primary objective: To determine the effects of high intensity stepping training on gait outcome measures in patients with cerebellar ataxia.

|€ Secondary objectives:

- Identify the correlations between gait outcome measures and measures of ataxia and balance in individuals with cerebellar ataxia.
- Determine differences in response to high intensity stepping training based off of diagnosis.

## Study Design

|€ The study will be a non-blinded prospective case series performed at TIRR Memorial Hermann and TIRR Kirby Glenn. Participants will be recruited if they have an ICD-10 code of ataxia or present with ataxia at initial evaluation. Either the director of the brain injury rehabilitation team or the evaluating therapist will contact the principal investigator in order to refer the patient to the study. The evaluating therapist will provide the PI with the referral through a secure e-mail utilizing their Memorial Hermann e-mail. The secure e-mail will include the patient diagnosis and their room number with no other personal identifiers listed until the patient consents to the research study.

|€ The study sample will be about 15 and the expected duration of the study will be at least 3-4 weeks.

|€ The primary outcomes measured include the 10 Meter Walk Test and the 6 Minute Walk Test. These outcome measures will be performed once at baseline and again at week 3.

|€ The secondary outcomes to be measured include the SARA and the Berg Balance Scale. These outcome measures will be performed once at baseline and again at week 3.

## Study Population

[figure not shown]
|€ The sample will consist of all patients with a diagnosis of ataxia who were admitted to TIRR TMC Inpatient or TIRR Kirby Glenn Outpatient. Diagnoses of inclusion will include any pathology that primarily affects the brain/ cerebellum including degenerative diseases, stroke, TBI, posterior fossa tumor, and MS. Additionally patients will be ambulatory at initial evaluation or will have functional ambulation goals at initial evaluation (as noted by 10 meter walk test and 6 minute walk test measures documented as 0). The ages that will be included

in this study are patients ages 18-65 years old and the chronicity of injury will be of at least 1 month or greater.

- |€ The exclusion criteria include diagnoses that may have cerebellar involvement but without cerebellar ataxia as a principal impairment such as autism, down syndrome, schizophrenia, etc. Additionally, patients who are nonambulatory or who are not able to participate in high intensity stepping training due to cardiac involvement (such as cardiac rehabilitation parameters) or due to orthopedic limitations (such as weight bearing parameters) will be excluded from the study.
- |€ The subjects will not be directly recruited. Subjects will be referred to do this study before or after their initial evaluation if they have an ICD 10 code indicating ataxia, are found to have gait ataxia, or have a neurologic injury to some part of their cerebellum based off imaging.

## Study Procedures

- |€ Potential subjects will be referred to the primary investigator upon arrival to TIRR Memorial Hermann Inpatient or TIRR Memorial Hermann Kirby Glenn outpatient, or after their initial evaluation is performed. The evaluating physical therapist will contact the primary investigator if a patient is presenting with physical symptoms of cerebellar ataxia. The evaluating physical therapist will contact the primary investigator through a secure email and will email [[contact]](mailto:[contact]). The e-mail will include secure in the heading, protecting patient information and data.
- |€ Informed consent will be obtained prior to participation in this study. The principal investigator will introduce the study to potential participants at initial evaluation or during their first physical therapy treatment session. Patients will be given the informed consent document and will be allowed to ask questions regarding the purposes, confidentiality, and procedures of the study.
  - If consent is obtained, all consent forms will be collected in a locked cabinet at the primary investigatorâ€™s desk.
- |€ The Six Minute Walk Test, 10 Meter Walk Test, SARA, and BBS will be recorded at initial evaluation and will also be collected by the primary investigator.
- |€ Each individual patient will receive 30 minutes of the high intensity stepping intervention 3 times a week for 3 weeks. Therefore, each participant will receive 9 sessions of high intensity stepping training, for a total of 4 hours and 30 minutes by the studyâ€™s conclusion.
- |€ Each intervention will occur with either the primary investigator as the physical therapist or as another Doctor of Physical Therapy providing care for that patient. If another Doctor of Physical Therapy is providing care for that patient, they will be instructed by the primary investigator on where to put interventions, heart rate monitoring, and blood pressure monitoring in the note. As the intervention is not extremely specific and since it is considered standard of care for patients with stroke, brain injury, and spinal cord injury, the primary investigator will not be required to be the only therapist providing the intervention for this study.
- |€ The intervention will require heart rate monitoring utilizing a â€œPolar H10â€¢ heart rate monitor, with the goal of reaching moderate to high intensity for 30 minutes during the one hour long therapy intervention. A screenshot of the Polar heart rate data will be taken after each session of monitoring and sent to the PI where it will be collected and kept in a private folder on a locked computer, with all patient information such as patient name transcribed to

a number [REDACTED] for confidentiality. The screenshots themselves will be off of the Polar heart rate app on the primary therapistâ€™s phone but will contain no patient identifiers. Once the screenshots are taken, they will immediately be sent to the researcher and then within 24 hours they will be uploaded to a folder as mentioned above in order to ensure no data is lost. To the right is an example of what a screenshot would look like (note no patient identifiers). In order to send this information to the primary investigator, this photo will be sent via a Secure e-mail with the picture of the heart rate data in addition to the date this data was collected and the patient that this data was collected for. Once the e-mail is sent, the screenshot will be deleted from the therapistâ€™s phone. The PI will then store this information on a locked computer as noted above.

- Link to product: <https://www.polar.com/us-en/sensors/h10-heart-rate-sensor?sku=92075957>
- Instructions for use: <https://www.youtube.com/watch?v=oN-RchX1UEQ>

|€ The treatment intervention will consist of overground walking, treadmill walking (with or without bodyweight support), stairs, resisted walking, and all other stepping/ gait training. The goal of treatment will be to increase the intensity of the exercise safely and to patient tolerance.

|€ For safety, patient blood pressure will be monitored before and after each session at the very least. In patients with history of hypertension, stroke, or orthostatic hypotension, it may be taken several times throughout the intervention. Additionally, the following will all merit the intervention to be stopped:

- A drop in systolic blood pressure >20 mmHg with the increasing workload
- An increase in systolic and/or diastolic blood pressure >180 mmHg or 110 mmHg, respectively.
- Reported chest or arm pain (angina)

- Severe shortness of breath, cyanosis, pallor, lightheadedness, dizziness or confusion

|€ The primary physical therapist will record all stepping interventions they performed in the treatment section of the note. The heart rate monitoring and heart rate data will be added in the treatment section of the note, below the actual treatment. Screen shots of the polar heart rate data for each patient will also be collected and stored in a coded file. Lastly, vitals before and after intervention will be recorded in the treatment section of the note under vitals.

|€ The 6 Minute Walk Test, 10 Meter Walk Test, SARA, and Berg Balance Scale will all be recorded again at discharge. There may also be additional walking measures weekly, depending on therapist preference, but physical performance measures will not count as a high intensity stepping intervention.

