### **Data and Safety Monitoring**

|€ For subjects who were not physically active prior to their neurologic injury, with intense exercise there is a possibility for increase in cardiovascular events such as stroke or heart attack.

|€ Patients with premorbid conditions will have close blood pressure and heart rate monitoring throughout the session by a skilled Doctor of Physical Therapy. There are physicians on site at TIRR Memorial Hermann in addition to skilled therapists that understand signs of poor exercise tolerance such as pallor, profuse sweating, headache, and lightheadedness. Patients with chest pain at any point during the study will have exercise immediately discontinued and will have all of their vitals signs including blood pressure, heart rate, and oxygen saturation checked on the spot. There are blood pressure cuffs and oxygen saturation monitors throughout all of the gyms and in all of the units at TIRR Memorial Hermann and TIRR Kirby Glenn.

|€ However, in the neurologic population that will be receiving the intervention, there is greater risk associated with remaining sedentary. Patients who do not receive intensive rehabilitation are at greater risk for pressure injury, deep vein thrombosis, Type 2 Diabetes, and obesity. Additionally, sedentary individuals are more likely to have low cardiorespiratory fitness, which is a well-known risk factor for chronic diseases.

|€ Additionally, literature published by the American Heart Association and the Neurologic Physical Therapy Association supports the implementation of high-intensity stepping training. Hornby et al has provided extensive research of high intensity stepping training on patients with stroke. Even though these patients have already had a cardiovascular-related event, even with interventions in which they are required to maintain their heart rate at 75-85% of HR Maximum, there were no increases in adverse events.

|€ Since this population will also be engaging in stepping training and locomotor training, there could be potential for increased risk of falls during interventions. However, therapists at the Memorial Hermann facility (which is where the study will be conducted) are highly experienced in walking interventions for these patients and in the prevention of falls. Additionally, most high intensity training stepping in patients with stroke, TBI, and SCI is proven to improve balance and thereby decrease risk of falls.

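### The study is labelled high intensity, but its session goal accepts moderate to high intensity, and no summary of intensity attained or sessions delivered is planned

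*Combined protocol and SAP*

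**What the plan says.** The title, Background Information (study goal and hypothesis), Objectives (primary objective) and the dose statement in Study Procedures all call the intervention high intensity stepping training. The dose statement says that "each participant will receive 9 sessions of high intensity stepping training, for a total of 4 hours and 30 minutes".

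Later in Study Procedures, the heart rate monitor is to be used "with the goal of reaching moderate to high intensity for 30 minutes during the one hour long therapy intervention". A second sentence there adds: "The goal of treatment will be to increase the intensity of the exercise safely and to patient tolerance".

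Therapists other than the principal investigator may deliver sessions. The only instruction named for them concerns documentation: "they will be instructed by the primary investigator on where to put interventions, heart rate monitoring, and blood pressure monitoring in the note".

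On records, Study Procedures says "A screenshot of the Polar heart rate data will be taken after each session of monitoring" and "Screen shots of the polar heart rate data for each patient will also be collected and stored in a coded file". Interventions are also written in the treatment note. The only rule on what counts as a session is that "physical performance measures will not count as a high intensity stepping intervention".

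The only heart-rate range appears in Data and Safety Monitoring, where patients in earlier stroke research are described as "required to maintain their heart rate at 75-85% of HR Maximum".

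The Statistics section plans a paired t-test of pre- and post-intervention outcomes, MANOVAs by diagnosis or chronicity, and a sample of 15. It mentions no summary of heart rate, minutes or sessions.

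**The concern.** Intensity is what gives this intervention its name. The list of activities in Study Procedures is open-ended and takes in any other stepping or gait training, so the type of activity does not define the treatment. Background Information also rests its rationale on intensity: the cited study suggesting a benefit of intensity used stationary cycling rather than walking.

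If the session goal can be met below the level in the title, the headline claims more than the plan requires. The design has one group, so no comparison arm would show what was delivered. Without a planned delivery summary, a reader of the results could not tell whether any change followed high, moderate or mixed intensity training. Interpreting the stored heart rate data would be left until the outcomes were known, with no categories agreed beforehand.

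**Working it through.** **Planned dose**

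Inputs: 30 minutes per session, 3 sessions a week, 3 weeks (Study Procedures); 1 hour 30 minutes a week (title page); 15 patients (Statistics).

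- Per week: 30 × 3 = 90 minutes = 1.5 hours, which agrees with the title page.
- Per patient: 3 × 3 = 9 sessions; 9 × 30 = 270 minutes = 4.5 hours, which agrees with Study Procedures.
- All patients: 15 × 9 = 135 sessions; 15 × 4.5 = 67.5 hours.

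The plan's dose figures are consistent with one another. The totals are planned values and not maxima, because Study Design says about 15 patients and the title page gives 3 weeks as a minimum.

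**Intensity wording side by side**

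| Place | Intensity |
|---|---|
| Title | high |
| Background Information, goal and hypothesis | high |
| Objectives, primary | high |
| Study Procedures, dose statement | high, for all 9 sessions |
| Study Procedures, session goal | moderate to high, for 30 minutes |
| Study Procedures, second goal sentence | raised as tolerated; no level named |

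The session goal can be read in two ways.

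1. As an acceptable range: a session held at moderate intensity throughout meets the goal.
2. As a progression from moderate towards high: some of the time is expected below high intensity.

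On neither reading does the goal require all 270 minutes to be at high intensity, so the mismatch with the dose statement remains either way.

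**Is the level defined elsewhere?**

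The 75-85% figure describes earlier research and supports a safety argument; it is not adopted as a target for this study. The instruction named for other therapists is about where to record. The counting rule excludes performance tests and says nothing about intensity. The example screenshot, case report form and study schedule are not visible and could not be checked.

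**Is a delivery summary planned?**

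- Recording: yes, heart rate and interventions at each session (Study Procedures).
- Review: yes, every two weeks (Data and Safety Monitoring) and weekly audits (Quality control and assurance).
- Reported summary: none in Statistics.

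The gap is in definition and reporting, not in data capture.

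**The case against.** The strongest reply is that the two goal sentences, read together, describe a progression towards high intensity, and that high intensity stepping training is simply the name of an established intervention. The plan also ties eligibility to that name by excluding patients who cannot take part for cardiac or orthopedic reasons. Delivery is limited to Doctors of Physical Therapy, and the principal investigator is described as the primary therapist documenting the interventions. Heart rate is stored, the data are reviewed regularly, and a descriptive table could be added at reporting without altering any test.

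Much of this is fair, and it limits the point. A progression is a reasonable reading, but it sets no level and does not make every planned minute high intensity. Eligibility and staffing rules do not define an intensity either.

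A reader might infer that intensity goes unchecked. The documents do not support that: reviews and audits are planned, although their stated purposes are safety and accurate data, and what is missing is a reported summary. A reader might also infer that no heart-rate target exists anywhere. That cannot be said while the example screenshot, case report form and study schedule are unseen. Even if those define zones, the two statements in Study Procedures would still differ and Statistics would still plan no delivery summary.

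**Conclusion.** The point holds as a mismatch between label and session goal, together with a missing reported summary. The label covers 270 planned minutes per patient and 135 planned sessions over 15 patients. Those figures show how much training carries the label, not how much would fall below it. The consequence is for what the study can conclude; no test, error rate or sample size changes.

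Two stronger inferences should be resisted. The first is that some share of sessions will stay moderate and be counted as high intensity. No rule excludes such a session, but none says it counts, and the documents give no figures from which to estimate a share. The second is that the primary objective's wording about effects should be changed as part of this point. What a single-group design can attribute to treatment is a separate question, and the goal sentence in Background Information speaks of effects too, so changing the objective alone would be selective.

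The conclusion rests on the visible text and assumes that the unseen attachments do not already contain both an adopted range and a planned delivery summary.

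**What to change.** - Reconcile the session goal with the title, Background Information, Objectives and the dose statement. Which intensity is right is for the investigators.
- Have the investigators set the intensity categories in writing before analysis.
- Add to Statistics a descriptive per-patient table from existing records: sessions delivered before the final tests against the planned 9, and intensity attained as far as the screenshots allow (time in each category if readable, otherwise average or peak heart rate).
- Word the conclusion by the intensity achieved.
- Reconcile Study Design, which puts the final tests at week 3, with Study Procedures, which puts them at discharge. Until then, sessions before the final tests cannot be counted consistently.

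The cost is wording changes, agreement on categories, and extraction of about 135 planned session records. No patients, visits or procedures are added. The downsides are a possibly more modest headline claim and the chance that time in category cannot be read from the screenshots.
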